2. OBJECTIVES AND ENDPOINTS

Objectives	Endpoints
Primary	

 To evaluate the TTR reduction of patisiran-LNP in hATTR amyloidosis patients with disease progression after OLT 	
 Average of Month 6 and Month 12 efficacy TTR percent reduction.
Secondary	

 To evaluate the effect of patisiran-LNP on neuropathy To evaluate the effect of patisiran-LNP on patient reported outcomes including QoL, activities of daily living and autonomic neuropathy symptoms To characterize the effect on nutritional status 	
 Change in the following parameters at 12 months 
 Neurologic impairment (NIS) Patient reported measures of QoL (Norfolk QoL-DN), activities of daily living (R-ODS) and autonomic symptoms (COMPASS-31) Nutritional status (mBMI)
Exploratory	

 To characterize exploratory measures of clinical activity (disease stage, functional status) To evaluate PK To assess for ADA against patisiran-LNP 	
 Change in the following parameters at 12 months 
 Disease stage (PND Score, FAP Stage) Functional status: KPS PK profile of ALN-18328, and the novel lipid excipients DLin-MC3-DMA and PEG₂₀₀₀-C-DMG Frequency and titer of anti-PEG₂₀₀₀-C-DMG ADA
Safety	

 To evaluate the safety and tolerability of patisiran-LNP in hATTR amyloidosis patients with disease progression after OLT 	
 Frequency of adverse events

3. INVESTIGATIONAL PLAN

3.1. Summary of Study Design

This is a global Phase 3b open-label study designed to evaluate the safety, efficacy, and PK of patisiran-LNP in patients with hATTR amyloidosis with disease progression after liver transplant. All eligible patients will be administered open-label patisiran-LNP.

Consented eligible patients enrolled in this study will receive 0.3 mg/kg patisiran-LNP IV once every 3 weeks for 12 months. Dosing is based on actual body weight. For patients weighing

100 kg or more, patisiran-LNP will be administered at a total dose of 30 mg IV once every 3 weeks. Eligibility for this study will be confirmed before administration of the first dose on Day 1.

Patisiran-LNP will be administered as an approximately 80-minute IV infusion (approximately 1 mL/minute for the first 15 minutes followed by approximately 3 mL/minute for the remainder of the infusion). In order to reduce the potential for an IRR with patisiran-LNP, all patients on this study will receive premedications at least 60 minutes before the start of the patisiran-LNP infusion. Patients who are tolerating their infusions well may be eligible to have a stepwise taper of the dose of corticosteroid premedication from 10 mg dexamethasone (or equivalent) to 5 mg during the study.

After the Day 1 visit, patients should return to the clinical site for patisiran-LNP dosing once every 3 weeks. Where applicable country and local regulations allow, eligible patients may receive the patisiran-LNP infusions at home by a healthcare professional trained on the protocol and delivery of premedications and patisiran-LNP.

Safety will be assessed throughout the study. Patients will return to the clinical site for safety evaluations at Week 12, 6 month efficacy visit, and 12 month efficacy visit. Patients will be continually assessed throughout the study for adverse events (AEs). Unscheduled visits for study assessments may occur if deemed necessary by the study personnel.

Efficacy assessments will be performed at baseline, 6 and 12 months.

3.2. Duration of Treatment

The duration of treatment with patisiran-LNP is 12 months.

3.3. Duration of Study Participants

It is anticipated that the duration of study participation for a subject or patient will be 14.5 months (inclusive of a 42-day screening period, 12-month treatment period, and a follow-up visit 4 weeks after the last dose of study drug.)

A patient is considered to have reached the end of the study when they have completed the follow up visit (4 weeks) after the last dose of patisiran-LNP.

3.4. Number of Planned Patients

The planned enrollment for this study is 20 patients.

3.5. Safety Review Committee

A safety review committee will not be utilized for this study; however, a transplant hepatologist will be available for consultation on an as needed basis.

4. SELECTION AND WITHDRAWAL OF PATIENTS

4.1. Inclusion Criteria

Patients are eligible to be included in the study if all the following criteria apply:

Age

1. Age 18 years (or age of legal consent, whichever is older) or older at the time of informed consent.

Patient and Disease Characteristics

2. Received an OLT for treatment of documented hATTR amyloidosis ≥ 12 months before the date of informed consent
3. A documented increase in polyneuropathy disability (PND) score (eg, a PND change from I to II, II to IIIA, or IIIA to IIIB) compared to a pre-liver transplant assessment OR a documented increase in PND score between any 2 assessments post-liver transplant, which in the opinion of the Investigator is due to underlying disease progression
4. On stable immunosuppressive regimen with ≤ 10 mg/day of prednisone for at least 3 months before the date of informed consent
5. Karnofsky performance status of $\geq 70\%$ at the time of consent
6. Vitamin A level greater than or equal to lower limit of normal at Screening Visit

Informed Consent

7. Willing and able to comply with the study requirements and to provide written informed consent, per local and national requirements.

4.2. Exclusion Criteria

Patients are excluded from the study if any of the following criteria apply:

Prior/Concomitant Therapy

1. Currently taking tafamidis, doxycycline, or tauroursodeoxycholic acid; if previously on any of these agents, must have completed a 14-day wash-out before dosing (Day 1)
2. Currently taking diflunisal; if previously on this agent, must have completed a 3-day wash-out before dosing (Day 1)
3. Received an investigational agent within the last 30 days of anticipated study drug administration or 5 half-lives of the study drug, whichever is longer, or are in follow-up of another clinical study before study enrollment
4. Current or past use of inotersen or patisiran-LNP

Medical Conditions

5. Liver allograft rejection episodes (chronic, acute, or subacute) or abnormal LFTs suggestive of possible allograft rejection in the past 6 months before the date of informed consent
6. Liver function test (including aspartate transaminase, alanine transaminase, and total bilirubin) results greater than upper limit of normal at the screening visit based on central laboratory evaluation. International normalized ratio (INR) > 1.2 for patients not on anticoagulant therapy; INR > 3.5 for patients receiving anticoagulant therapy
7. Known portal hypertension with ascites

8. Estimated glomerular filtration rate ≤ 30 mL/min/1.73 m² (calculated by a central laboratory using the Modification of Diet in Renal Disease formula) at screening visit
9. Other known causes of sensorimotor or autonomic neuropathy (eg, autoimmune disease)
10. Known leptomeningeal amyloidosis
11. Uncontrolled diabetes (episodes of diabetic ketoacidosis or hyperglycemic, hyperosmolar nonketotic coma within the prior 9 months)
12. Active infection with hepatitis B or hepatitis C at screening visit (based on serology at central laboratory)
13. Known human immunodeficiency virus (HIV) infection based on patient's medical history
14. Hospitalizations for infections in prior 3 months from the time of informed consent, and no active infections at screening or baseline
15. New York Heart Association (NYHA) classification of >2 at screening visit
16. PND score IV (wheelchair bound or bedridden)
17. Hospitalizations for congestive heart failure or arrhythmia in the past 3 months before the date of informed consent
18. Malignancy within the last 5 years from the time of informed consent, except for basal or squamous cell carcinoma of the skin or carcinoma in situ of the cervix that has been successfully treated
19. Has other medical conditions or comorbidities which, in the opinion of the Investigator, would interfere with study compliance or data interpretation
20. Unable to comply with requirements of study including premedications required prior to patisiran-LNP infusions
21. Exclude patients with organ transplants other than liver transplant

Contraception, Pregnancy, and Breastfeeding

22. Is not willing to comply with the contraceptive requirements during the study period, as described in Section 5.5.1. (NOTE: Contraception is not required in males.)
23. Female patient is pregnant or breastfeeding.

Alcohol Use

24. Unwilling or unable to limit alcohol consumption throughout the course of the study. Alcohol intake of >2 units/day is excluded during the study (unit: 1 glass of wine, [approximately 125 mL] = 1 measure of spirits [approximately 1 fluid ounce] = $\frac{1}{2}$ pint of beer, approximately 284 mL).
25. History of alcohol abuse, within the last 12 months before screening, in the opinion of the Investigator.

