		D-42 to -1	Pre-Dose Day 1	D1	W1-2	W3 ±3D	W6 & 9 ±3D	W12 ±3D	W15 to 21 ±3D	W24 ±3D	W25 to WK 26±3D	W27 to W33 ±3D	W36 ±3D	W39 to W51 ±3D	W54 ±3D	W55 to W56	W57	Not applicable
Informed Consent		X																
Inclusion/Exclusion Criteria		X	X															
Medical History	See Section 6.1	X	X															
Demographics		X																
HIV Status Review	Section 6.1.3	X																
Height		X																
NYHA Classification			X															
Karnofsky Performance Status		X								X					X		X	
PND Score and FAP Stage		X								X					X		X	
NIS			X							X					X		X	
Norfolk-DN QoL			X							X					X		X	
R-ODS			X							X					X		X	
COMPASS-31			X							X					X		X	

Table 1: Schedule of Assessments

Study Day (±Visit Window)	Notes	Screening	Baseline ^a	Dosing							6-Month Efficacy	Dosing				12-Month Efficacy	Early Termination	Safety Follow Up
		D-42 to -1	Pre-Dose Day 1	D1	W1-2	W3 ±3D	W6 & 9 ±3D	W12 ±3D	W15 to 21 ±3D	W24 ±3D	W25 to WK 26±3D	W27 to W33 ±3D	W36 ±3D	W39 to W51 ±3D	W54 ±3D	W55 to W56	W57	Not applicable
Echocardiogram with Doppler		X																
12-Lead ECG	See Section 6.1.7	X																
NT-proBNP		X																
mBMI	See Section 6.2.6.		X							X					X		X	
Serum samples for TTR Protein	See Section 6.2.1		X		X	X				X	X			X	X			
Serum samples for anti-drug antibody	See Section 6.3.3.1		X			X				X				X				
Plasma samples for PK	See 2		X	X	X	X				X				X	X	X	.	
Pregnancy Test	See Section 6.3.3.2, Section 6.3.5.7, and Table 3	X	X			X	X	X	X	X	X	X	X	X			X	
Exploratory DNA Sample (optional)	See Section 6.5		X															

Table 1: Schedule of Assessments

Study Day (±Visit Window)	Notes	Screening	Baseline ^a	Dosing							6-Month Efficacy	Dosing				12-Month Efficacy	Early Termination	Safety Follow Up	
		D-42 to -1	Pre-Dose Day 1	D1	W1-2	W3 ±3D	W6 & 9 ±3D	W12 ±3D	W15 to 21 ±3D	W24 ±3D	W25 to WK 26±3D	W27 to W33 ±3D	W36 ±3D	W39 to W51 ±3D	W54 ±3D	W55 to W56	W57	Not applicable	W58 ±3D
Exploratory Biomarkers (plasma, serum)		X									X				X				
Full Physical Exam	See Section 6.3.2	X									X				X		X		
Symptom-Directed Physical Exam	See Section 6.3.2		X																
Vital Signs	See Section 6.3.1	X	X	X		X	X	X	X	X	X	X	X	X	X		X		
Serum samples for Vitamin A	See Section 6.1.1	X																	
Serum Chemistry, including LFTs	See Section 5.2.4.1	X	X (albumin only)					X			X		X		X		X		
Hematology		X						X			X		X		X		X		
Adverse Events	See Section 6.3.5.2				Continuous														

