Concomitant Medications and Procedures	See Section 5.3	X			Continuous														
Liver Allograft Status	See Section 6.3.4	X						X			X		X		X		X		

Table 1: Schedule of Assessments

		Screening	Baseline ^a	Dosing							6-Month Efficacy	Dosing				12-Month Efficacy	Early Termination	Safety Follow Up	
				D-42 to -1	Pre-Dose Day 1	D1	W1-2	W3 ±3D	W6 & 9 ±3D	W12 ±3D		W15 to 21 ±3D	W24 ±3D	W25 to W26 ±3D	W27 to W33 ±3D				W36 ±3D
Study Day (±Visit Window)	Notes																		
Weight	See Section 6.1.4		X	X		X	X	X	X	X	X	X	X	X	X	X		X	
Premedication and Study Drug Administration	Phone contact for home infusions only			X		X	X	X	X	X		X	X	X	X				

Abbreviations: COMPASS=Composite Autonomic Symptom Score; DNA=deoxyribonucleic acid; ECG=electrocardiogram; FAP=familial amyloidotic polyneuropathy; HIV=human immunodeficiency virus; LFT=liver function test; M=month; mBMI=modified body mass index; NIS=neurological impairment scale; NYHA=New York Heart Association; NT-proBNP=N-terminal prohormone of B-type natriuretic peptide; PK=pharmacokinetic; PND=paroxysmal nocturnal dyspnea; QoL= quality of life; R-ODS=Rasch-built Overall Disability Scale; TTR=transthyretin; W=week.

Notes: The Screening visit must be performed within 42 days before the first dose of study drug (Day 1).

Early termination visit should occur within 7 days of the decision to stop participating in the study.

Table 2: Pharmacokinetic Time Points

Study Visit	Day 1	Week 1-2	Week 3	Week 24	Week 54	Week 55-56	Week 57
Pre-Dose	X		X	X	X		
End of Infusion	X			X	X		
4 ± 1 h post EOI	X				X		
24 ± 4 h post EOI	X				X		
72 ± 6 h post EOI	X				X		
Day 7 to Day 14 post EOI		X				X	
Day 21 post EOI							X

TABLE OF CONTENTS

PROTOCOL SYNOPSIS	4
TABLE OF CONTENTS.....	13
LIST OF TABLES	16
LIST OF FIGURES	16
LIST OF ABBREVIATIONS AND DEFINITIONS OF TERMS.....	17
1. INTRODUCTION.....	19
1.1. Disease Overview	19
1.2. Patisiran-LNP (ALN-TTR02).....	20
1.3. Study Design Rationale	20
1.4. Dose Rationale.....	21
1.5. Benefit-Risk Assessment.....	21
2. OBJECTIVES AND ENDPOINTS.....	23
3. INVESTIGATIONAL PLAN.....	23
3.1. Summary of Study Design.....	23
3.2. Duration of Treatment	24
3.3. Duration of Study Participants.....	24
3.4. Number of Planned Patients	24
3.5. Safety Review Committee	24
4. SELECTION AND WITHDRAWAL OF PATIENTS.....	24
4.1. Inclusion Criteria	24
4.2. Exclusion Criteria	25
4.3. Removal from Study Drug or Assessment	27
4.3.1. Discontinuation of Study Drug or Declining Procedural Assessments	27

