6.1. Screening and Baseline Assessments

An informed consent form (ICF) that has been approved by the appropriate Institutional Review Board (IRB)/Independent Ethics Committee (IEC) must be signed by the patient before the Screening procedures are initiated. All patients will be given a copy of the signed and dated ICF.

Patients will be screened to ensure that they meet all the inclusion criteria and none of the exclusion criteria. Patient demographic data and medical history/disease history will be obtained. Any changes to medical history occurring between the screening assessment and Day 1 will be updated before study drug administration. An interval medical history will be collected at the Screening and Baseline visit. Only changes since the Screening visit will be collected. Medical history will capture transplant history and evidence for disease progression.

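### The Day 1 eligibility check has no new scheduled liver test, so the scheduled LFT baseline is a screening value up to 42 days old; criterion 15 and Table 1 disagree on when NYHA class is assessed

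*Protocol*

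**What the plan says.** **Entry criteria (Protocol 4.1 and 4.2).** Criterion 5 covers rejection episodes or "abnormal LFTs suggestive of possible allograft rejection in the past 6 months before the date of informed consent". Criterion 17 covers "Hospitalizations for congestive heart failure or arrhythmia in the past 3 months before the date of informed consent". Inclusion 4 requires a stable immunosuppressive regimen "for at least 3 months before the date of informed consent". Criterion 6 excludes AST, ALT or total bilirubin "results greater than upper limit of normal at the screening visit based on central laboratory evaluation". Criterion 15 excludes "New York Heart Association (NYHA) classification of >2 at screening visit".

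**Schedule (Table 1).** Screening, including consent, runs from Day -42 to Day -1. The serum chemistry row, which carries the LFTs, is marked at Screening. Its Baseline (pre-dose Day 1) cell reads "X (albumin only", and its next mark is Week 12. Liver Allograft Status is marked at Screening and then at Week 12. NYHA classification is marked at Baseline and not at Screening.

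**Checks before dosing.** Table 1 marks the inclusion/exclusion review at both Screening and Baseline. Protocol 3.1 has eligibility confirmed before the first dose. Protocol 6.1 adds: "Any changes to medical history occurring between the screening assessment and Day 1 will be updated before study drug administration".

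**Analysis.** SAP 3.4 takes as baseline the last evaluable value on or before the first dose. SAP 4.5.3 counts ALT or AST above 3 x ULN and rejection events as AEs of clinical interest (AECIs). SAP 4.5.4 tabulates shifts from baseline to the worst post-baseline category.

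**The concern.** The criteria most specific to liver transplant recipients are fixed at consent or screening, while treatment may start up to six weeks later. The Day 1 review applies the same wording, so it has no newer liver result to look at, and an event after consent falls outside the look-back windows.

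Two things are at stake. The first is clarity: two sites could treat the same screening-period rejection episode or heart failure admission differently and both be following the protocol. The second is attribution. Liver enzyme rises and rejection are the study's designated AECIs, and there is no control arm to show the background rate. If the only scheduled pre-treatment liver result is weeks old, a rise that began before treatment looks the same as one that began on it.

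**Working it through.** The plan gives no figure on this point. Its one computed design figure, a 95% CI half-width of about 10% with n = 16 and SD 18%, reproduces (t = 2.131; 2.131 x 18/√16 = 9.59) and is not affected.

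**Step 1. Where each criterion ends, compared with Day 1.**

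| Criterion | Ends at | Scheduled new information on Day 1 |
|---|---|---|
| Inclusion 4, stable immunosuppression | Consent | History update; no allograft status |
| 5, rejection or suggestive LFTs | Consent | History update; no LFT, no allograft status |
| 6, AST/ALT/bilirubin above ULN | Screening | None |
| 15, NYHA above 2 | Screening (text) | NYHA is recorded on Day 1 only |
| 17, heart failure or arrhythmia admission | Consent | History update |
| 1 and 2, washouts | Day 1 | Already anchored to dosing |
| 14, active infection | Screening or baseline | Already reaches baseline |

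The last two rows show that the protocol anchors criteria to Day 1 or baseline elsewhere. For criteria 5 and 17 and inclusion 4, an event on Day -20 after an earlier consent is recorded in the history but lies outside the window as worded. Criterion 19 has no time anchor and could be used, on the investigator's judgement that the condition would interfere with compliance or data interpretation.

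**Step 2. Gap between scheduled LFTs.** Inputs from Table 1: screening 1 to 42 days before Day 1; Week 12 = 84 days after Day 1, window ±3 days.
- Longest: 42 + 84 + 3 = 129 days.
- Shortest: 1 + 84 - 3 = 82 days.
- Longest nominal gap: 42 + 84 = 126 days, of which 42/126 = 33% precedes the first dose.
- Infusions between the two samples: Day 1 and Weeks 3, 6 and 9, so four. Week 12 is the fifth dosing day.

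**Step 3. What the SAP does with this.** With no LFT scheduled on Day 1, the last scheduled pre-dose value is the screening one. Criterion 6 requires AST, ALT and total bilirubin to be no higher than ULN in that sample. A silent rise beginning on, say, Day -10 and still present at Week 12 would appear in the shift table as a move from not elevated to high. If it exceeded 3 x ULN, it could be counted as an AECI on treatment.

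**Step 4. Effect of a Day 1 panel.** The 126-day nominal gap splits into at most 42 days before treatment and 84 days on treatment (81 to 87 with the window). A rise is then placed before or after the first dose. It is not dated more closely within Weeks 0 to 12.

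**Step 5. Scale.** With 20 patients, one event on the wrong side of Day 1 moves an incidence by 1/20 = 5 percentage points. The documents give no rate of screening-period liver events, so no probability can be attached to this.

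**The case against.** A reader might infer that patients who become ineligible during screening will be dosed. The documents do not support that. Eligibility is reviewed again at Baseline and confirmed before the first dose, interval history is taken, criterion 19 allows exclusion, and Protocol 4.3 lets the investigator or sponsor stop study drug at any time. What stands is narrower: exclusion for an interval event is discretionary, and the review has no new scheduled LFT.

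A reader might also infer that early liver events cannot be dated at all. Protocol 6.3.5.2 records SAEs from consent and puts other pre-dose events in the medical history, so a clinically evident rejection episode during screening would be documented as pre-treatment. SAP 3.11 lets unscheduled visits supply baseline values, so an unscheduled pre-dose LFT would replace the screening one. The problem is confined to silent rises seen in scheduled samples. As the SAP would score them, such rises add to the on-treatment count, so they would not conceal harm.

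On NYHA, a reader might infer that the cardiac check stops at screening. Table 1 shows the reverse, since the only scheduled assessment is on Day 1. The defect is a contradiction between the criterion and the schedule.

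Finally, counting look-backs from consent can be a legitimate choice, and the first on-treatment LFT stays at Week 12 whatever is done on Day 1. Both points are fair. The first is why the windows should be reconciled by the sponsor and not rewritten by a statistician. The second limits what the Day 1 panel can deliver.

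**Conclusion.** The point holds in this limited form. Criteria 5 and 17 and inclusion 4 end at consent and criterion 6 at screening, up to 42 days before Day 1, and the Day 1 confirmation has no new scheduled LFT to work with. The gap between scheduled LFTs is 82 to 129 days and spans four infusions, so scheduled samples alone cannot place a silent Week 12 rise before or after the first dose. Criterion 15 and Table 1 contradict each other on NYHA.

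This rests on the Table 1 marks as printed, and on no unscheduled LFT being taken between screening and Day 1. The 42 days and the 5 percentage points describe exposure and scale; they are not estimates of how often misattribution would occur. The sample size and the primary TTR analysis are untouched. It is worth acting on because the correction is cheap and bears on the study's designated liver safety events.

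**What to change.** 1. In Table 1, extend the Baseline chemistry cell to the LFT panel of Table 3 (AST, ALT, ALP, total and direct bilirubin), run on the pre-dose sample already drawn. Keep albumin, which baseline mBMI needs. SAP 3.4 would then select this value for the shift tables without rewording. In SAP 4.5.3, report it beside each ALT or AST AECI, so that a rise already present before dosing is visible.
2. Reconcile criterion 15 with the NYHA row of Table 1, so that the criterion applies at the visit where NYHA class is recorded.
3. Have the sponsor reconcile the consent and screening anchors of criteria 5, 6 and 17 and inclusion 4 with the Day 1 confirmation in Protocol 3.1, and state whether events between consent and Day 1 count. The same text should say whether the Day 1 panel is for baseline only or must be available before dosing. The documents give no central laboratory turnaround time, and without a result in hand the panel serves as a baseline but not as an eligibility check.

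Cost: one added panel per patient on an existing sample, and wording changes in the protocol and SAP. If the sponsor makes Day 1 findings count, there may be an occasional late screen failure or delayed Day 1.

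### Exclusion criterion 14 reverses direction in mid-sentence, so as written it does not exclude a patient for having an active infection

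*Protocol*

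**What the plan says.** Protocol section 4.2 opens with the rule that governs all 25 items: "Patients are excluded from the study if any of the following criteria apply". Section 6.1 repeats the direction: "Patients will be screened to ensure that they meet all the inclusion criteria and none of the exclusion criteria". Criterion 14 in that list is "Hospitalizations for infections in prior 3 months from the time of informed consent, and no active infections at screening or baseline".

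Two other exclusion criteria name specific infections. Criterion 12 is limited to hepatitis B or C at the screening visit, and criterion 13 to "Known human immunodeficiency virus (HIV) infection". Criterion 14 is the only line in section 4.2 that mentions active infection in general, and none of the seven inclusion criteria in section 4.1 mentions infection. The synopsis, Administrative Change 1 and the SAP do not restate or correct the criterion.

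**The concern.** Under an exclusion heading, a listed condition that is true of a patient keeps that patient out. Recent hospitalisation for infection works that way. Having no active infection does not: it is a condition an eligible patient should satisfy, so the sentence changes direction at the comma.

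The protocol itself makes infection relevant. Section 1.1 names infection as a risk of the lifelong immunosuppression that transplant patients need, and as one of the usual causes of death in this disease. Inclusion criterion 4 requires a stable immunosuppressive regimen, and the premedication in section 5.2.2 includes intravenous dexamethasone. Section 3.5 states that no safety review committee is used. At stake is whether sites apply the same rule to a patient who has an active infection at screening or baseline. The wording also matters for deviation review: SAP section 2.2 counts any departure from protocol procedures as a deviation, and as major if it may affect patient safety. Enrolling an infected patient with no recent hospitalisation would be a departure under one reading of criterion 14 and not under another.

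**Working it through.** No figure in the plan depends on this point, so the check is one of logic. Let H be hospitalisation for infection in the 3 months before consent, and I an active infection at screening or baseline. Under the opening sentence of section 4.2, a patient is kept out when the criterion is true. Criterion 14 can be read in three ways:

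1. **Conjunction**, following the word *and*: kept out if H and not I.
2. **Two separate exclusions**: kept out if H, or if not I.
3. **Exclusion plus requirement**, the likely intent: kept out if H, and also kept out if the requirement of no active infection fails, that is, if H or I.

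| Patient | Reading 1: H and not I | Reading 2: H or not I | Reading 3: H or I |
|---|---|---|---|
| Hospitalised, infected | not kept out | kept out | kept out |
| Hospitalised, not infected | kept out | kept out | kept out |
| Not hospitalised, infected | not kept out | not kept out | kept out |
| Not hospitalised, not infected | not kept out | kept out | not kept out |

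- Reading 1 keeps out the recently hospitalised patient who has recovered and lets in the one who is still infected. It differs from reading 3 in 2 of 4 rows, which are both rows with an active infection.
- Reading 2 keeps out every patient without an active infection, so it cannot be used in practice. It also differs from reading 3 in 2 of 4 rows.
- The infected patient with no recent hospitalisation is kept out only under reading 3. That reading needs words the criterion lacks, such as a statement that the second clause is a requirement.

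Other lines in the list are loosely drafted too, but each states its own direction. Criteria 1 and 2 contain a requirement inside an exclusion and say that the wash-out must have been completed. Criterion 21 reads "Exclude patients with organ transplants other than liver transplant". Criterion 24 reads "Alcohol intake of >2 units/day is excluded during the study". Criterion 17, the parallel item on cardiac hospitalisation, is a plain exclusion with nothing appended. The second clause of criterion 14 has no such cue.

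Administrative Change 1 amends sections 5.2.2.1, 6.3.5.2 and 6.5 only.

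**The case against.** The strongest reply is that the meaning is easy to infer. Readings 1 and 2 both give perverse results, which leaves one sensible reading, and most investigators would probably adopt it. The list already mixes exclusions with requirements in criteria 1 and 2, so a reader could take criterion 14 in the same way.

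There are also other safeguards. Criteria 12 and 13 cover hepatitis and HIV, and criterion 19 leaves room for the investigator's judgement. Table 1 schedules a full physical examination, haematology, vital signs and a concomitant medication review at Screening. At Baseline it schedules a second eligibility check, vital signs and a symptom-directed examination, which section 6.3.2 directs at new or changed symptoms. Section 4.3 allows study drug to be discontinued in the patient's best interest. No eligibility checklist is among the documents, so nothing shows that a site applied the literal wording. Enrolment status is not stated either, so a correction might come too late to affect any patient.

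Most of this stands, and it limits the weight of the point. It does not make the sentence right. The perversity of reading 1 is itself evidence that the criterion is wrong as written. The scheduled checks may reveal an infection, but they do not say whether it excludes the patient. Criterion 19 is confined to interference with compliance or data interpretation.

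**Conclusion.** The concern holds, as a minor point. Criterion 14 is wrong as written: under its own heading it does not exclude a patient because of an active infection, and its likely intent has to be inferred. The defect is one clause in 1 of 25 exclusion criteria. No numerical effect is claimed, because the documents give no frequency of active infection at screening or baseline. The sample size (16 evaluable, about 20 enrolled) and the analyses do not depend on it.

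Confidence is high for the wording and its logic. Any practical consequence rests on an assumption that the documents cannot confirm: that some sites would apply the literal text, or would differ in how they resolve it.

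**What to change.** The sponsor should reconcile criterion 14 with the opening sentence of section 4.2. It should confirm the intended rule, then word each clause, as one item or two, so that its direction is unambiguous under an exclusion heading. Any eligibility checklist should be aligned with the corrected wording. Which clinical rule applies is for the sponsor to decide.

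The cost is one sentence in a protocol amendment or administrative clarification. Administrative Change 1 (29 Oct 2018) already used that route to clear up other inconsistencies in this protocol. No change to the SAP is needed. If enrolment has already closed, the sponsor can still record the intended rule, so that eligibility deviations are judged against a single reading.
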